## 8.7.3. Clinical Laboratory Evaluation

Laboratory data values will be converted to International System of (SI) units by conversion programming (detail can be found in the database conversion specifications) and delivered to the analysis and reporting group in SI units. A list of the SI units used to present laboratory data is provided in Appendix 1.

Laboratory parameters, ECOG, vital signs and ECG will be presented by tumor group for each dose cohort and within each tumor group at baseline, at each posttreatment time point before maintenance phase, and at the end of study. Data starting at the maintenance phase will be included in the summary of maximum and minimum for all visits, which will present the largest and smallest values observed for each patient posttreatment visits and the visit at the end of study.

#### 8.7.3.1. Hematology

The following hematology tests will be summarized: hemoglobin, hematocrit, platelet count, red blood cell (RBC) count, and white blood cell (WBC) total count, WBC differential (basophils, eosinophils, lymphocytes, monocytes, and neutrophils).

Descriptive statistics will be provided for each test result and for change from the baseline by visit. Multiple measurements taken during the visit for a patient will be presented by the most severe value for each hematology test. The most severe value will be determined first by the value closest to the upper or lower limit of the normal limits (dependent on which direction is considered severe) if the value is within the normal limits. If the value is outside the normal limits, the value furthest from the upper or lower limit will be selected (dependent on which direction is considered severe). In the event that this algorithm does not allow for determining the most severe (i.e., a tie, etc.) the first chronological value will be selected. Low values are considered the most severe for all hematology analytes.

A by-patient listing will be provided and will flag values outside of the reference range for each lab variable.

## 8.7.3.2. Chemistry

The following chemistry tests will be summarized: alanine transferase (ALT), alkaline phosphatase (ALP), aspartate transferase (AST), bicarbonate, bilirubin (total, direct, indirect), blood urea nitrogen (BUN), calcium, chloride, creatinine, glucose, magnesium, phosphorus, potassium, protein (total), sodium, uric acid, and albumin.

Descriptive statistics will be provided for each test result and for change from baseline by visit. Multiple measurements taken during the visit for a patient will be presented by the most severe value as noted in Section 8.7.3.1. For all chemistry analyses, the most severe could be in either direction for glucose, potassium, sodium, calcium, and magnesium. For these analytes, if within the normal limits, the value closest to the normal limits (either direction) is selected. If outside the normal limits, the value most distant from the normal limits (either direction) will be used.

A by-patient listing will be provided and will flag values outside of the reference range for each lab variable.

## 8.7.3.3. Urinalysis

A by-patient listing will be provided and will flag values outside of the reference range for each lab variable. Parameters to be collected and displayed are blood glucose, ketones, leukocyte esterase, nitrites, and pH. Protein microscopic examination will be conducted if blood or protein is 2+ or higher.

#### 8.7.3.4. Other Tests

Other tests will be listed including hepatitis B antigen, hepatitis C antibody, serum pregnancy ( $\beta$ -human chorionic gonadotropin) (in female patients of child-bearing potential only), HIV-1 antibody, and HIV-2 antibody.

## 8.7.3.5. CTCAE Coding of Laboratory Data

Where laboratory values are categorized into NCI CTCAE version 4.0 grades, the categories are defined according to the criteria available on the following website:

http://evs.nci.nih.gov/ftp1/CTCAE/About.html

Note that grades are applied based only on the numeric value of the parameter assessed; clinical signs and symptoms are not considered. For example, Grade 4 hyperglycemia will be assigned based solely on the value of the glucose measurement, and acidosis will not be considered. Where categories are only distinguished by clinical signs or symptoms, the lowest of the possible grades will be assigned that do not involve the clinical sign or symptom described. Grade 0 means normal.

NCI CTCAE grades will be applied for the following lab parameters (given in Appendix 2):

- Hematology: hemoglobin (anemia, hemoglobin increased), total WBC (leukopenia), lymphocytes (lymphopenia), neutrophils (neutropenia), and platelets (thrombocytopenia).
- Chemistry: albumin (hypoalbuminemia), alkaline phosphatase, ALT, AST, total bilirubin, calcium (hypocalcemia, hypercalcemia), creatinine, glucose (hyperglycemia, hypoglycemia), magnesium (hypermagnesemia, hypomagnesemia), phosphorus (hypophosphatemia), potassium (hyperkalemia, hypokalemia), and sodium (hyponatremia, hypernatremia).

A summary of maximum severity observed on-study for all parameters noted above will be generated for the coded hematology and chemistry parameters. Patients will only be included once, in the maximum severity, for each laboratory parameter. Additionally, a shift summary of baseline to maximum severity on-study will also be produced. Patients with at least 1 on-study measurement for each laboratory parameter will be included, regardless of whether or not a baseline assessment is present (baseline will be included as a missing category). Thus, percentages for each parameter will be based on the total number of patients with an on-study measurement for the parameter of interest.

Laboratory measurements that are within their institutional limits of normal and are not graded as 1-4, per the CTCAE, will be summarized as "Grade 0," which is defined as normal.

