#### Part 2:

- Vaccine Induction Phase: once every 7 days for 8 weeks (doses 1 9)
- Consolidation Phase: once every 14 days for 10 weeks (doses 10 − 15 [maximum of 6 doses])
- Maintenance Phase: once every 28 days until discontinuation (dose 16 and thereafter)

Figure 1: **Study Schematic – Part 1** Consolidation End of Disease Progression/Survival **Screening** Vaccine Maintenance Phase Study Induction Phase Phase Dosing once within Dosing once every 14 days 28 days within Dosing once every 28 days for 6 weeks after last 21 days every 7 days until (doses 6 - 9) dose and for 4 weeks before first discontinuation prior to dose (doses 1 - 5) (dose 10 and start of thereafter) alternative antineoplas tic therapy **DLT** Evaluation Every 3 Period months Days 1 to 29

Figure 2: Study Schematic – Part 2

The following dose cohorts are planned for this study.

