# 8. STATISTICAL ANALYSIS

In this section and all after, when tables are presented by posttreatment visits, the last visit will be the visit at the end of study. When applicable, visits after the start of the maintenance phase and unscheduled visits will be included in a summary of maximum and minimum values observed for each patient's posttreatment visits, i.e., the minimum and maximum values are based on all the post treatment visits.

In general descriptive statistics for continuous variables will be summarized by the mean, standard deviation, 25th percentile, median (50th percentile), 75th percentile, minimum and maximum values. When continuous variables are displayed for less than 3 patients, only the number of observations will be presented. Categorical variables will be summarized using counts and percentages.

All raw data will be presented to the original number of decimal places. The means and medians will be presented to 1 more decimal place than the raw data. The standard deviations will be presented to 2 more decimal places than the raw data.

Baseline will generally be defined as data obtained as the last non-missing value prior to the first dose of study drug, i.e., including the pre-dose assessment on Day 1, assessments during screening and other assessments prior to the first dose of study drug.

AE tables and laboratory tables will be presented by visits and by tumor group. Tumor groups are defined as groups of overall, solid tumor, and AML patients.

Unless otherwise stated, summaries will be produced by dose cohort, which is defined as the intended and starting dose to which the patient was enrolled.

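### Worst-grade, shift and minimum/maximum laboratory tables cannot be compared between Part 1 and Part 2 dose cohorts, because after Day 29 the parts differ in scheduled draws and doses

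*SAP*

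**What the plan says.** SAP Section 8.7.3.5 takes one result per patient and parameter, the worst CTCAE grade: "A summary of maximum severity observed on-study for all parameters noted above will be generated for the coded hematology and chemistry parameters". It adds a shift table from baseline to that worst grade. The period is called on-study, with no last day or visit set. The denominator counts patients, not draws or time: "percentages for each parameter will be based on the total number of patients with an on-study measurement for the parameter of interest".

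The columns come from the default rule in Section 8: "Unless otherwise stated, summaries will be produced by dose cohort, which is defined as the intended and starting dose to which the patient was enrolled". Section 8.7.3 adds tumor group: "Laboratory parameters, ECOG, vital signs and ECG will be presented by tumor group for each dose cohort". Section 8 also says that "the minimum and maximum values are based on all the post treatment visits", and Section 8.7.3 extends this to late data: "Data starting at the maintenance phase will be included in the summary of maximum and minimum for all visits".

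Section 4.1 gives the two parts different schedules. Part 1 (0.3 to 9.0 mg) has five weekly doses, four doses at 14-day intervals, then one every 28 days. Part 2 (18.0 and 27.0 mg only) has "Vaccine Induction Phase: once every 7 days for 8 weeks" (nine doses), then up to six doses at 14-day intervals, then one every 28 days. Hematology and chemistry are scheduled on dosing days (Tables 1 to 4).

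**The concern.** The more often a patient is measured, the worse the worst value tends to be, even with no drug effect. All patients at 18.0 and 27.0 mg are on the denser schedule and all patients at lower starting doses are on the sparser one. A difference in worst grade between those two sets of columns could therefore reflect dose, extra doses, extra draws or different time on study, and the table cannot separate these.

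The tables bear on the primary safety objective. Sections 6.2 and 8.7.1 set the overall safety profile beside DLT incidence, and worst-grade laboratory tables are an obvious source for it. Nothing in the SAP limits them to common visits, shows the number of draws, or warns that the schedules differ.

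**Working it through.** **The plan's own dose counts.** Doses per phase = (length in days / interval) + 1.
- Part 1: 28/7 + 1 = 5 and 42/14 + 1 = 4.
- Part 2: 56/7 + 1 = 9 and 70/14 + 1 = 6.

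These agree with Section 4.1.

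**Scheduled draws after the first dose,** from Tables 1 to 4. The Day 1 draw precedes dosing and is baseline. Part 1 maintenance is placed at its nominal 28-day interval.

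| Up to | Part 1 draw days added | Part 2 draw days added | Draws, Part 1 v 2 | Doses, Part 1 v 2 |
|---|---|---|---|---|
| Day 29 | 8, 15, 22, 29 | 8, 15, 22, 29 | 4 v 4 | 5 v 5 |
| Day 57 | 43, 57 | 36, 43, 50, 57 | 6 v 8 | 7 v 9 |
| Day 85 | 71, 85 | 71, 85 | 8 v 10 | 9 v 11 |
| Day 141 | 113, 141 | 99, 113, 127, 141 | 10 v 14 | 11 v 15 |

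The Day 29 draw precedes the fifth dose, so the window from first dose to before the fifth dose holds 4 doses and 4 draws in both parts.

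**Caveat on Day 141.** The hematology row of Table 4 is broken after Day 99 in the text available. A draw at every dosing visit is the likelier reading. The row for continuation criteria breaks in the same way although dosing is marked at every visit, and Section 8.7.3 expects maintenance laboratory data. If Days 113, 127 and 141 had no draw, the count would be 10 v 11. Counts to Day 85 are legible.

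**Effect of draw count alone.** The documents give no chance q that a single draw shows a given grade. I assume it is equal in both parts and show a range. With n independent draws, P(at least one) = 1 − (1 − q)^n. By Day 141:

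| q | n = 10 | n = 14 | Gap (points) |
|---|---|---|---|
| 0.5% | 4.9% | 6.8% | 1.9 |
| 1% | 9.6% | 13.1% | 3.6 |
| 2% | 18.3% | 24.6% | 6.3 |
| 5% | 40.1% | 51.2% | 11.1 |
| 10% | 65.1% | 77.1% | 12.0 |

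The gap between a and b draws peaks at 1 − q = (a/b)^(1/(b − a)).
- Day 141: (10/14)^(1/4) = 0.919, so q is about 8% and the gap is 0.431 − 0.308 = 12.3 points, or about 1.2 patients in a cohort of 10.
- Day 57: the peak is 10.5 points.
- Day 85: the peak is 8.2 points.
- Day 29: the gap is zero at every q.
- With 10 v 11 draws by Day 141, q = 5% gives 40.1% v 43.1%.

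**Correlated draws.** Results from one patient resemble each other. In a beta-binomial model with intraclass correlation r, P(at least one) = 1 − B(α, β + n)/B(α, β), where α = q(1 − r)/r and β = (1 − q)(1 − r)/r. The 10 v 14 gap becomes:

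| r | q = 2% | q = 5% |
|---|---|---|
| 0 | 6.3 | 11.1 |
| 0.1 | 3.0 | 6.0 |
| 0.3 | 1.2 | 2.7 |
| 0.5 | 0.6 | 1.4 |

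**Unequal time on study.** Section 2 lets patients stay until progression, intolerance or another discontinuation criterion.
- Part 1 to Day 85 and Part 2 to Day 57 both have 8 draws, so there is no gap.
- Part 1 to Day 169 (11 draws) against Part 2 to Day 57 (8 draws) gives 19.9% v 14.9% at q = 2%, so the gap reverses.

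**The case against.** The strongest reply is that the direction of the bias is not established and little rests on it. Most of this stands.

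- **Direction.** Higher grades in Part 2 follow only for equal time on study, which the tables do not ensure. Section 4.1.3.2 also lets Part 1 patients move up to Part 2 doses, while Section 8 keeps them in their starting-dose column. That can push the other way. Footnotes to Tables 3 and 4 let some Part 2 patients leave the extended phases early, which can lower their draw count.
- **Decisions.** A reader might infer that the MTD is at risk. The documents do not support that. The MTD definition and the escalation rules (Sections 4.1, 4.1.1 and 4.1.2) use DLT counts in Days 1 to 29, where the schedules match. Sections 6.2 and 8.7.1 add the overall safety profile but do not name this table.
- **Existing safeguards.** Laboratory values and changes are summarized by visit before maintenance (Sections 8.7.3 to 8.7.3.2). DLTs are tabulated by grade (8.7.1), and exposure duration and cumulative dose by cohort (8.5). None of these gives a worst grade over a common window or shows draw counts. Section 8.5 also describes only the Part 1 dose counts, 5 and 4, against 9 and up to 6 in Section 4.1 for Part 2; these must be reconciled.
- **Adverse events.** The per-draw arithmetic does not carry over to TEAEs, which are spontaneously reported (6.6). Events caused by the extra Part 2 doses are real effects of that regimen. Tables by last dose received are already planned (8.7.2), but laboratory grades have no counterpart.
- **Tumor mix.** Part 2 is limited to glioblastoma and AML. Protocol Amendment No. 6 expects baseline cytopenias in AML and removes hematological entry criteria for those patients. Equal schedules alone therefore do not make the six dose levels alike.

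What survives is that an uncapped worst-grade table, by starting dose, mixes two schedules without saying so.

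**Conclusion.** The all-study worst-grade, shift and minimum/maximum laboratory tables are not comparable between Part 1 and Part 2 cohorts. Comparisons within Part 1, or of 18.0 with 27.0 mg, share a schedule, although time on study can still differ.

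For equal time beyond Day 29, draw count alone biases worst grades upward in Part 2. The bias is at most about 12 points per parameter by Day 141. That bound assumes independent draws, the same per-draw risk in both parts, full adherence to the schedule, and the reading of Table 4 with 14 draws. Correlation within patients makes it smaller.

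A reader might go further and infer that 18.0 and 27.0 mg will look more toxic by schedule alone. The documents do not support this: time on study is open-ended and dose increases stay in the starting-dose column, so the gap can shrink, vanish or reverse. Nor are the extra doses a mere artefact of measurement. They are real exposure, confounded with dose level. DLT counts are unaffected. The change is worth making because it is cheap and the plan has no worst-grade comparison on equal doses and draws.

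**What to change.** In Sections 8.7.3.5 and 8.7.2, add as a supplement the maximum-grade, shift and TEAE tables by dose cohort and by tumor group, limited to the DLT Evaluation Period (first dose to before the fifth dose). Doses and scheduled draws are then the same in both parts, and dose increases, allowed only after consolidation, cannot enter. The TEAE version is justified by equal dosing, not by draw counts.

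Keep the all-study tables for late and cumulative toxicity; the restricted version should not become the sole basis for comparing doses. In the all-study tables, define on-study, show the median number of draws and weeks on study per cohort, and add a note that dose and schedule are confounded between parts and that tumor mix also differs.

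The cost is a few extra tables from existing programs with a date filter. The restricted tables omit late events, and they do not remove differences in tumor mix, which the tumor-group split addresses only in part.

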## 8.7.4. Electrocardiograms

A standard 12-lead ECG will be used to collect and record electrocardiographic data according to the schedule of assessments. Parameters to be collected include ventricular heart rate, QT interval, PR interval, QRS duration, and RR interval (ms). The corrected QT interval will derived according to the Fridericia formula

$$QT_{c-F} = QT / (RR - RR/1000)^{1/3}$$

as well as Bazett's formula

$$QT_{c-B} = QT / (RR - RR/1000)^{1/2}$$
.

The descriptive statistics for the ECG parameters and changes from predose Day 1 will be summarized by dose cohort at each time point prior to the start of the maintenance phase, end of study and the maximum and minimum observed values on study.

The number and percent of patients with QTc-F values in the following ICH E14 categories will be summarized by dose cohort:

- $QT_{c-F} \ge 500$  ms at any postdose time point and not present at baseline
- $QT_{c-F} \ge 450$  ms at any postdose time point and not present at baseline
- Change from baseline in  $QT_{c-F} \ge 60$  ms for at least 1 postdose measurement
- Change from baseline in  $QT_{c-F} \ge 30$  for at least 1 postdose measurement, but < 60 ms for all postdose measurements

The similar table will be presented for QTc-B.

The patients in the following categories will be presented in patient listings: overall, rhythm, conduction, morphology, myocardial infarction, and the presence of ST, T, and U wave abnormalities.

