# 1. LIST OF ABBREVIATIONS AND DEFINITIONS OF TERMS

Term	Description
β - HcG	β-human chorionic gonadotropin
AEs	Adverse event
ALP	Alkaline phosphatase
ALT	Alanine transferase
AML	Acute myeloid leukemia
AST	Aspartate transferase
BMI	Body mass index
BUN	Blood urea nitrogen
CA-125	Cancer antigen 125
CI	Confidence interval
CR	Complete remission
CRc	Composite complete remission
CRi	Complete remission with persistence of cytopenias
CRF	Case report form
CT	Computed tomography
CTCAE	Common Terminology Criteria for Adverse Event
CTL	Cytotoxic T lymphocyte
CTMS	Clinical trials management system
DLT	Dosing-limiting toxicity
DOR	Duration of response/remission
DTH	Delayed-type hypersensitivity reaction
ECG	Electrocardiogram
ECOG	Eastern Cooperative Oncology Group
ELISA	Enzyme-linked immunosorbent assay
HLA	Human leukocyte antigen
HSCT	Hematopoietic stem cell transplantation
ICH	International Conference on Harmonisation of Technical
	Requirements for Registration of Pharmaceuticals for Human Use
IHC	Immunohistochemistry
IPD	Important Protocol Deviations
irCR	Immune-related complete response
irPD	Immune-related progressive disease
irPR	Immune-related partial response
irRC	Immune-related response criteria
irSD	Immune-related stable disease
IWG	Modified International Working Group
KM	Kaplan Meier

MedDRA	Medical Dictionary for Regulatory Activities
MTD	Maximum tolerated dose
NCI	National Cancer Institute
OS	Overall survival
PBMC	Peripheral blood mononuclear cell
PD	Progressive disease
PFS	Progression-free survival
PR	Partial response/remission
PT	Preferred term
$QT_{c-B}$	Corrected QT interval, using Bazett's (square root) correction
$QT_{c-F}$	Corrected QT interval, using Fridericia's (cube root) correction
RBC	Red blood cell
RP2D	Recommended phase 2 dose
RT-PCR	Reverse transcriptase-polymerase chain reaction
SAE	Serious adverse event
SAP	Statistical Analysis Plan
SD (2)	Standard deviation; Stable disease
SE	Standard error
SOC	System Organ Class
SI	International System of Units
SPD	Sum of the product of the 2 largest perpendicular diameters
TEAE	Treatment-emergent adverse event
TTP	Time to progression
US	United States
WBC	White blood cell
WHO	World Health Organization
WT1	Wilms' tumor gene 1

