# 6.2. Primary Endpoint Variables

The safety and tolerability of WT2725 Dosing Emulsion will be evaluated based on the occurrence of DLT and AEs, and the findings from clinical laboratory tests, vital signs measurements, body weight measurements, and ECG results.

The determination of the MTD of WT2725 Dosing Emulsion will be based on the incidence of DLT at each dose escalation cohort and the overall safety profile of WT2725 Dosing Emulsion. The incidence of DLT will be evaluated during the DLT Evaluation Period.

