## 8.7. Analysis of Safety

## 8.7.1. Dose-Limiting Toxicity (DLT)

The primary endpoint is based on the incidence of DLT at each dose cohort and the overall safety profile of WT2725 Dosing Emulsion. The incidence of DLT will be evaluated during the DLT Evaluation Period, which extends from the day of the first dose to just prior to the fifth dose of study drug (Days 1 to 29). No more than 4 doses of study drug will be administered during the DLT Evaluation Period.

DLTs are defined as any Grade 3 or greater AE that occurs after the administration of study drug during the DLT Evaluation Period that are not related to underlying disease, intercurrent illness, or concomitant medications. (Changes in hematology parameters need to have been confirmed on repeat assessment and constitute at least a 2 grade shift. Grade 3 AEs of nausea, vomiting, and fatigue that are common and manageable in cancer patients will not be considered DLT if they can be ameliorated to < Grade 3 with standard supportive care management.) AEs will be graded according to the CTCAE.

The number and percentage of patients will be presented for DLT and non-DLT by each dose cohort during the DLT evaluation period. Specific DLTs are flagged in the collection of AE data and will be listed.

The number and percentage of DLT events will be presented by dose cohort and for all patients. The DLTs observed for the DLT evaluation period will be summarized by dose cohort and for all subjects by MedDRA SOC and PT. DLTs will also be summarized by category of NCI CTCAE grade.

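### The QTc formulas in SAP 8.7.4 do not convert RR from ms to seconds, so QTcF comes out about 10 times and QTcB about 32 times too small

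*SAP*

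**What the plan says.** SAP Section 8.7.4 (Electrocardiograms) lists the parameters to be collected, ending with "QRS duration, and RR interval (ms)", so RR is on the millisecond scale. It then gives two derivations. QTcF is "QT / (RR - RR/1000)^{1/3}" and QTcB is "QT / (RR - RR/1000)^{1/2}"; they differ only in the exponent, one third against one half.

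These values feed two kinds of output:

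- Summaries by visit: "The descriptive statistics for the ECG parameters and changes from predose Day 1 will be summarized by dose cohort".
- Counts of patients with a newly occurring QTcF of at least 450 ms or at least 500 ms, a change from baseline of at least 60 ms, or a change of at least 30 ms that always stays below 60 ms. A similar table is planned for QTcB.

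Section 1 (List of Abbreviations) defines QTcF as "Corrected QT interval, using Fridericia's (cube root) correction" and QTcB as the corresponding Bazett square-root correction. Appendix 2 starts QTc Grade 1 at 450 ms. Section 6.2 includes ECG findings among the primary safety variables: "the findings from clinical laboratory tests, vital signs measurements, body weight measurements, and ECG results".

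**The concern.** Both corrections scale QT to a heart rate of 60 beats per minute, that is, to RR = 1 second. The quantity under the root must therefore be close to 1 for an ordinary heart rate. The printed bracket subtracts one thousandth of RR from RR, which leaves a number close to 1000 when RR is in ms. The 1000 has an evident purpose, converting ms to seconds, but the printed expression does not do that.

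If the analysis programs follow the text, every derived QTc value is wrong for every patient at every visit. The less obvious harm is in the category tables. They would be almost empty in each dose cohort, which reads as a clean ECG result, so real prolongation would not show there. Safety and tolerability is a primary objective of this dose-escalation study.

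**Working it through.** **Inputs.** RR in ms, the two printed formulas, and the cut-offs 450, 500, 30 and 60 ms are all from SAP 8.7.4. The intended corrections (cube root, square root) are from SAP Section 1. The SAP gives no worked QTc value to reproduce. The QT and RR values below are illustrative assumptions.

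**Step 1: simplify the bracket.** RR − RR/1000 = RR × (1 − 0.001) = 0.999 × RR, still in ms.

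**Step 2: compare with RR in seconds.** The usual divisor is (RR/1000)^k, with k = 1/3 or 1/2. The ratio of correct to printed value is

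(0.999 × RR)^k / (RR/1000)^k = 999^k,

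which depends on neither QT nor RR:

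- QTcF: 999^(1/3) = 9.997
- QTcB: 999^(1/2) = 31.61

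**Step 3: numerical examples (all in ms).**

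| QT | RR | QTcF correct | QTcF printed | QTcB correct | QTcB printed |
|---|---|---|---|---|---|
| 400 | 1000 | 400.0 | 40.0 | 400.0 | 12.7 |
| 400 | 800 | 430.9 | 43.1 | 447.2 | 14.2 |
| 480 | 900 | 497.2 | 49.7 | 506.0 | 16.0 |
| 480 | 800 | 517.1 | 51.7 | 536.7 | 17.0 |

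**Step 4: true value needed to be counted.** Each cut-off is multiplied by the factor from Step 2.

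| SAP cut-off | True QTcF needed (ms) | True QTcB needed (ms) |
|---|---|---|
| Change ≥ 30 ms | 300 | 948 |
| Change ≥ 60 ms | 600 | 1,896 |
| Level ≥ 450 ms | 4,498 | 14,223 |
| Level ≥ 500 ms | 4,998 | 15,803 |

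**Step 5: range of printed values.** Over RR 500 to 1500 ms and QT 360 to 480 ms, printed QTcF runs from 31.5 to 60.5 ms and printed QTcB from 9.3 to 21.5 ms. Going from the lowest to the highest corner of that grid changes printed QTcF by only 60.5 − 31.5 = 29.0 ms, which is still below the 30 ms category.

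**Step 6: does the unit of RR matter?** If RR were entered in seconds, the printed formulas would be almost right: 0.999^(−1/3) = 1.00033 and 0.999^(−1/2) = 1.00050, so 0.03% and 0.05% too high. The error therefore rests on RR being in ms, which is what Section 8.7.4 states. Neither the SAP nor the protocol text supplied contains another QTc formula or a conversion of RR.

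**The case against.** The strongest objection is that the whole point turns on one character. The text was extracted from a PDF, and displayed equations survive that badly; the Wilson interval in SAP Section 7.1 also looks damaged, with the root running over the denominator. A line that originally set RR equal to RR/1000 would turn into exactly this string if the equals sign were read as a minus. That the sign appears in both formulas does not settle it, because the same glyph would be misread the same way twice. This stands as a condition: the original page has to be checked.

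Second, the intent is plain. The corrections are named, Section 1 describes them, and the cut-offs are on the usual scale. A programmer would probably use the standard formulas, and a mean QTcF near 40 ms should be noticed. Whether any output was derived wrongly cannot be told from the documents. That lowers the chance of harm but does not make the stated derivation right, and a SAP should not depend on someone silently overriding it.

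Third, the reach is limited, and this stands in full. The DLT definition works through graded adverse events ("DLTs are defined as any Grade 3 or greater AE that occurs after the administration of study drug"), and no DLT, MTD or escalation rule uses the QTc categories. SAP 8.7.3.5 applies CTCAE grades only to laboratory parameters, so the QTc row in Appendix 2 shows the expected scale but drives no stated analysis. Uncorrected QT, RR, heart rate, the ECG abnormality listings and adverse events are unaffected. Because the factor is constant, the ordering of patients is kept, and QTc can be re-derived from the collected QT and RR.

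**Conclusion.** The concern holds on the text as it stands. Section 8.7.4 specifies a derivation that cannot give values on the scale of its own categories: QTcF is too small by a factor of 9.997 and QTcB by 31.61, at every QT and RR. All QTc summaries and changes would be wrong, and the 450/500 ms and 30/60 ms tables would be empty for practical purposes.

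The conclusion rests on three things: RR is in ms, as the SAP states; the minus sign is on the original page; and the formulas are programmed as printed. It is most likely a slip in two well-known formulas rather than a choice of method. It should still be corrected before analysis, because the derived QTc tables are part of the ECG evidence for the primary safety evaluation.

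**What to change.** 1. Check the operator in both formulas on the original SAP page.
2. If it is a minus, replace the formulas with QTcF = QT / (RR/1000)^(1/3) and QTcB = QT / (RR/1000)^(1/2), and state that QT and RR are in ms.
3. Check the programmed derivation against these formulas. QT 400 ms with RR 1000 ms must return 400 ms for both; QT 480 ms with RR 900 ms must return 497.2 ms (QTcF) and 506.0 ms (QTcB).
4. Add a plausibility range check on derived QTc, so that a unit error is caught before the tables are produced.

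The cost is two lines of SAP text and a short check of the code. No new data are needed.
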